4.1 Study Participants

Subjects will be parents/caregivers and their children in grades K-4 in one of three Counties: Cuyahoga County (East Cleveland City School District (ECCSD, Cleveland, OH) and Bedford City School District (BCSD, Bedford, OH)); Cowlitz County (CC, WA); and Lewis County (LC, WA); (See Table 4.1.1 below). The study will be offered to all caregivers and their children including those children with special health care needs. Parent/caregivers and children will be enrolled in the study upon signing the consent/assent form and completing the recruitment and contact form. All enrolled children will receive a dental screening at the beginning of the school year. Following the screening, only parent/caregivers whose child has a tooth with an International Caries Detection and Assessment System (ICDAS) active lesion score of 2 or greater will be randomized and continue further participation in the trial. Caregivers with multiple children in K-4 will receive the same intervention assignment.

Table 4.1.1 School District Information

County	School District	Elementary Schools	K-4 Enrollment
Cuyahoga Co.	East Cleveland City SD	Caledonia, Chambers, Mayfair, Superior	889
	Bedford City SD	Central, Glendale, Columbus, Carywood	1274
Cowlitz Co.	Kelso SD.	Catlin, Wallace	1122
	Longview SD.	Kessler, St. Helens	
Lewis Co.	Central SD.	Jefferson Lincoln	586
	Winlock SD.	Winlock Miller	

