5.4 Treatment Assignment Procedures

5.4.1 Randomization Procedures

Sequence Generation: The study Biostatistician will generate the randomization sequence, which will be loaded into REDCap for allocation. REDCap is a secure, web-based application designed to support remote data capture for research studies, providing: 1) an intuitive interface for validated data entry, 2) audit trails for tracking data manipulation and export procedures, 3) automated export procedures for seamless data downloads to common statistical packages, and 4) procedures for importing data from external sources. Caregivers will be randomly assigned to one of the five study arms in the 17:17:2:2:17 ratio; randomization of caregivers will be stratified by their child's grade level and school. The caregivers with multiple children will receive the same treatment based upon the grade level and school of one of their children, selected at random. Permuted blocks will be used to ensure the allocation of treatment assignments within strata as planned. Only the Biostatistician and the Data Manager will be aware of the blocking scheme and the actual assignments.

Allocation Process: Caregivers will be allocated to study arms using the randomization module provided in REDCap. REDCap uses previously-generated randomization sequences to assign records to study arms, and can support up to 14 stratifying variables. Each unique caregiver ID will be linked to one or more unique child IDs in a one-to-many relationship. As each child record is examined, the corresponding caregiver's study arm assignment will be displayed. If no allocation is found, the study staff will be directed to the randomization form to allocate that caregiver to the correct arm. REDCap will assign each caregiver to a specific study arm in accordance with the pre-determined randomization sequence and the stratifying variables. To assist study staff in quickly processing randomizations, stratifying variables (as well as other basic data) will be prepopulated into REDCap by the Project Coordinators, using information gathered prior to the dental screening and randomization process. REDCap is secured using TLS/SSL, enabling study staff to use it from laptops using public or private wireless connections.

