12.2 Sample Size Considerations

The primary aims are to compare dental care receipt among the five intervention groups, overall and separately for each study site (Ohio and Washington).

The five intervention groups are:

Arm 1: CSM referral letter alone (N=204)

Arm 2: CSM referral letter + DIG (N=204)

Arm 3: Reduced CSM referral letter alone (N=24)

Arm 4: Reduced CSM referral letter + DIG (N=24)

Arm 5: Modified Standard letter (N=204)

The utilization will be defined as evidence of dental care through restorations or extractions at the final study visit exam that was previously not found during the baseline exam. All changes will be recorded on a tooth level using ICDAS criteria and then dichotomized at the caregiver level as having obtained or not obtained dental care for their child/children.

There are three treatment comparisons to assess the overall CSM referral letter and DIG: CSM referral letter alone versus standard letter (Arm 1 vs Arm 5), CSM referral letter plus DIG versus standard letter (Arm 2 vs Arm 5), and CSM referral letter alone versus CSM referral letter plus DIG (Arm 1 vs Arm 2). As described below we address the issue of multiple testing, both multiple comparisons and multiple sites, using a gatekeeper approach. By specifying a sequence of tests, this approach will allow for the use of a nominal 0.05 alpha level for each test while maintaining a 0.05 family-wise alpha level for the six tests (three at each study site).

An additional comparison will be conducted to assess the effect of the targeted component (e.g., the ‘timeline’ text): CSM referral letter with and without DIG versus reduced CSM referral letter with and without DIG (Arm 1, 2 vs Arm 3, 4).

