The sample size was calculated with the following assumptions for the overall effect of the intervention letter: 19% utilization rate for standard letter (Nelson et al. 2012), 37% rate for CSM referral letter alone (based on Medicaid utilization among children: GAO-08-1121, 2008), 57% rate for CSM referral letter + DIG (based on 57% who reported that they took their child to the dentist or had an appointment after receiving the CSM referral letter + DIG in the R34 study). Then, using a two-sided test for equal proportions (namely, a Z test with pooled variance), we find that a sample size of 102 per intervention group per site (thus, 306 subjects per site) will provide 80% power to detect rate differences of 19% versus 37% (as expected for Arm 5 vs Arm 1) or 37% versus 57% (as expected for Arm 1 vs Arm 2) for each site, and 98% power for each of these comparisons using the

combined sample. As siblings (with the same caregiver) may be included in the study, a conservative approach will be to consider the required sample sizes as referring to the number of caregivers. Somewhat greater power will be expected if within-caregiver correlation is less than 1.

For the Ohio site with a total of 889 potential children, we expect 86% to participate (Nelson & Milgrom 2012), with 56% receiving a referral and 5% excluded for emergent needs. From previous [name] study in ECCSD elementary schools we expect 10% of caregivers to have multiple (usually two) children. Thus, an estimated total of 366 caregivers will be available for randomization to the five groups. For the Washington sites, with a total of 1704 potential children, we expect 85% participation (based on 2013 screenings in both districts), with 28% receiving a referral, 5% exclusions for emergent needs, and a 10% reduction in the corresponding number of caregivers due to inclusion of siblings. A total of 347 caregivers will be available for randomization. Even with 5% out of school transfers, the available sample will be adequate for testing the proposed hypothesis. Thus, we expect to randomize 330 caregivers/site to the five study arms to account for any drop-outs at randomization and maintain the required power for the trial.

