12.4 Final Analysis Plan

Primary Statistical Analysis: Descriptive statistics will include frequencies (categorical variables) and means (continuous variables) of baseline covariates among the five intervention groups. Chi-square tests (for categorical variables) and t-tests (for continuous variables) will be performed to test for group differences (by site and overall). In our primary analysis, we will fit multivariate generalized linear (specifically, logistic regression) models with dental care receipt as the (binary) outcome and the child as the unit of analysis (as receipt of dental care will be determined for each child). A generalized estimating equations (GEE) approach (with an exchangeable working correlation structure) will be used to allow for correlations among multiple children for a given caregiver. Separate models will be fit for each site as well as overall. The models will include two indicator variables representing the three interventions. Each model will include an a priori selected set of

baseline variables (listed below) and, for the overall model, an indicator variable for site. Secondarily, we will fit a model with a site by intervention group interaction, and the latter will be tested to formally assess possible intervention effect heterogeneity over sites.

We will also consider working correlation structures (e.g., alternating logistic regressions) that allow for second-level clusters, namely schools (within which the first-level cluster, caregiver, is nested). We will determine final models based on the quasi-likelihood information criterion (QIC). Intervention (and other covariate) effects will be tested using generalized score statistics.

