Given the parameter estimates from the above models, we use a model-based standardization approach (Albert et al. 2011) to estimate relative risks (i.e., the ratio of the probabilities of dental usage for a given pair of interventions). A bootstrap approach will be used to obtain a 95% confidence interval for each relative risk. Significance will be determined using a gatekeeper approach to hypothesis testing. Specifically, we will first test for a difference in dental care receipt rates for S vs CSM+DIG (at the 0.05 nominal alpha level). If (and only if) this test is significant, we will proceed to test S vs. CSM alone and CSM vs CSM+DIG (both at the 0.05 nominal alpha level). We will use a similar approach for testing for each site. We will start by testing (for a given treatment comparison) an overall effect (stratifying over sites) at the 0.05 nominal alpha level. If (and only if) this is significant, we will then test (for the same treatment comparison) the effect within each site (at the 0.05 nominal alpha level). A 0.05 family-wise error level is attained in this approach assuming that a (true) effect for S vs. CSM+DIG implies a (true) effect for either S vs. CSM or CSM vs. CSM+DIG (or both), and that an overall effect implies an effect in one or both sites (which is logically the case).

To test the effect of the targeted component (timeline), we will fit the same multivariate generalized linear (specifically, logistic regression) models mentioned above with additional indicator representing reduced text.

Adjustment for Baseline Characteristics: Estimated intervention effects (described above) will be adjusted for the following baseline socio-demographic variables: child's age, race, and caregiver SES, education, and marital status.

Model Assumptions: We will assume that the probabilities of dental care receipt follow the selected logistic regression model (controlling for covariates) mentioned above. We assume that the outcomes for different caregivers (or different schools if a correlation structure for two cluster levels is used) are independent.

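### Section 12.4 lets QIC make the 6 to 8 schools per site the independent units of the score tests; if it does, per-site power falls from the stated 80% to about 50-65%

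*Combined protocol and SAP*

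**What the plan says.** Section 12.4 (Final Analysis Plan) fits logistic GEE models with the child as unit of analysis and an exchangeable correlation within caregiver, separately by site and overall. It then widens the choice: "We will also consider working correlation structures (e.g., alternating logistic regressions) that allow for second-level clusters, namely schools". The selection rule is "We will determine final models based on the quasi-likelihood information criterion (QIC"), and the test is fixed in the next sentence: "Intervention (and other covariate) effects will be tested using generalized score statistics".

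Under Model Assumptions the same section gives the consequence. Outcomes for different caregivers ("or different schools if a correlation structure for two cluster levels is used) are independent". It states no small-sample correction.

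Three other places bear on this:

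- **Randomisation (5.4.1).** Caregivers are randomised individually, stratified by grade and school. A family with several children is placed in a stratum "based upon the grade level and school of one of their children, selected at random".
- **Number of schools (Table 4.1.1).** East Cleveland has four ("Caledonia, Chambers, Mayfair, Superior") and Bedford four, so Ohio has 8. Washington has 6, or 7 if the entry Jefferson Lincoln is two schools.
- **Aims and power (12.2).** The primary aims compare arms "overall and separately for each study site (Ohio and Washington"). With 102 caregivers per arm per site, the plan claims "80% power to detect rate differences of 19% versus 37% (as expected for Arm 5 vs Arm 1) or 37% versus 57" percent at each site, and 98% for the combined sample.

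**The concern.** The sample size in section 12.2 treats caregivers as independent. Section 12.4 allows the trial data to replace roughly 300 independent units per site with 6, 7 or 8. An empirical-variance score test behaves very differently with so few units, and section 12.2 gives no power for that case.

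School-level clustering also buys little here. Each school contains all the main arms, so differences in level between schools do not bias or destabilise the arm comparison. At stake are the per-site tests of the letter alone and of adding the Dental Information Guide. On the school branch a real effect of the planned size would be missed 35-50% of the time rather than 20%.

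**Working it through.** **1. The plan's own figure.** Inputs from 12.2: rates 19%, 37% and 57%; 102 per arm per site; two-sided 0.05; pooled-variance Z test. Power = Φ{[|p₁−p₂|√n − 1.96√(2p̄q̄)] / √(p₁q₁+p₂q₂)}.

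- 19% vs 37%: (0.18×10.10 − 1.96×0.635)/0.622 = 0.92, power 82.2%.
- 37% vs 57%: (0.20×10.10 − 1.96×0.706)/0.692 = 0.92, power 82.1%.
- After the 5% transfers mentioned in 12.2, 102×0.95 ≈ 97 per arm, which gives 80%. With 204 per arm, power is 98%.

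The stated figures therefore reproduce.

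**2. The score statistic with K schools.** Let U_k be school k's contribution to the score for the tested arm effect. The one-degree-of-freedom generalized score statistic is T = (ΣU_k)²/ΣU_k². By Cauchy-Schwarz, T ≤ K. If t is the one-sample t statistic of the U_k, then T = K·t²/(t²+K−1). Requiring T > 3.84 means t² > 3.84(K−1)/(K−3.84).

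For power, take t as noncentral on K−1 df with noncentrality 0.18/√[(0.1539+0.2331)/102] = 2.92. For 37% vs 57%, 0.20/√[(0.2331+0.2451)/102] is also 2.92.

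| K | required abs(t) | actual size | power, either comparison |
|---|---|---|---|
| 6 | 2.98 | 3.1% | 53% |
| 7 | 2.70 | 3.6% | 61% |
| 8 | 2.54 | 3.9% | 65% |

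**3. Simulation of the school branch.** Settings: individual randomisation within school, equal school sizes, school effect SD 0.3 on the logit scale (assumed).

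| Comparison | Caregiver as unit | 6 schools | 7 schools | 8 schools |
|---|---|---|---|---|
| 19% vs 37% | 82-83% | 51-53% | 58-61% | 63-65% |
| 37% vs 57% | 84% | 54% | 60% | 65% |

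- Varying the school SD from 0 to 0.6 moves these figures by about 2 points at most. The loss comes from the small number of clusters, not from an intraclass correlation.
- Unequal school sizes (assumed Dirichlet, parameter 4) lower 19% vs 37% to 39%, 49% and 55%.
- Combined sites, with 14 or 15 schools: about 96% against 98%. Per-site 19% vs 57%: at least 98%.
- An exchangeable GEE score test clustered on school gave 51-55% (6 schools) and 63-68% (8 schools).

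**4. How often QIC takes that branch.** QIC's penalty uses the robust variance, which is biased downward with few clusters. In an 8-parameter model with no school effect, the median penalty trace was 6.7-7.3 with school clusters and 8.1-8.4 with caregiver clusters. QIC therefore leans toward the school structure even when schools do not matter. It chose that structure in 80-83% of simulated site trials with no school effect, 66-71% at SD 0.3 and 37-40% at SD 0.6.

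**5. The whole planned procedure** (QIC choice, then score test), 19% vs 37%, 306 caregivers per site, 10% with two children:

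- At SD 0.3: 67% (6 schools), 70% (7), 75% (8).
- Across SD 0 to 0.6: 62-79%.
- Caregiver clustering in the same runs, with or without school indicators: 84-86%.

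**The case against.** **The 50-65% is conditional.** Caregiver clustering is the starting model and school structures are only to be considered. This stands: averaged over QIC's choice, the shortfall from 80% at SD 0.3 is 5 to 13 points, not 15 to 30. How often QIC picks schools also depends on assumptions that the documents do not supply.

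**Caregiver clustering is not valid for every target.** If letter effects vary between schools and the inference is meant to reach beyond these schools, the caregiver-level test rejects too often. With zero average effect and an assumed school-slope SD of 0.3 on the logit scale, it rejected 6.5% (6 schools) and 6.3% (8). At SD 0.5 it rejected 9.2% and 7.9%, while the school-level test stayed at 3.1-4.0%. This stands as a limit, but the plan does not set that wider target. With 6 to 8 chosen schools per site, inference about the participating schools is the natural reading.

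**A correction may be in the separate SAP** listed under Supplemental Materials. That is possible; section 12.4 states none. Using a t reference instead of chi-square would not restore the power. At the noncentrality that gives 80% (2.80), power would be 61% with 6 schools and 67% with 8, against 50% and 62% uncorrected.

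**The affected tests come late.** Per-site tests run only after the combined test of the same comparison succeeds, and those combined tests are safe. That limits the damage, but 12.2 lists the site comparisons among the primary aims and sizes the trial for them.

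**Enrolment may not reach 306 at each site.** Section 5.3 reports low enrolment at both sites and describes a second year of recruitment in the Ohio districts. This qualifies the 80% baseline but does not rescue the school branch.

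**Conclusion.** The concern holds. Section 12.4 leaves the independent unit of a primary test to a data-driven criterion, and one permitted outcome contradicts the power stated in 12.2. The bound T ≤ K and the conditional power of about 50-65% are firm, because they barely depend on the size of any school effect; equal school sizes are the favourable case. The unconditional 62-79% is softer. It rests on an assumed school SD of 0 to 0.6, equal school sizes, a caregiver random-effect SD of 1, covariates with no effect, and a two-level exchangeable correlation standing in for alternating logistic regressions. It was run for 19% versus 37% only.

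Type I error is not inflated; the school-level test is conservative, at 3.0-3.9%. The combined-site conclusions are not threatened. This should be corrected before analysis, but it does not invalidate the trial.

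**What to change.** Pre-specify for all primary tests:

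- GEE with caregiver as the only independent cluster, with QIC not used to choose the clustering level.
- School, a randomisation stratum, entered as a covariate, pooling schools with very few events by district. For sibling families, use the school of the child drawn for stratification. Grade is optional because child's age is already in the model.
- A statement that inference concerns the average effect in the participating schools.
- Any two-level school structure reported as a labelled sensitivity analysis.

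This changes the analysis wording only; enrolment, randomisation and data collection stay as they are. The price is 5 to 7 more parameters in each site model. With them, simulated power was 84-86% and null rejection about 5%. The remaining exposure is the effect variation between schools described above, which the sensitivity analysis would help to show.

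### The two-way gatekeeper does not hold the stated 0.05 family-wise error over the six site-level tests when effects differ between Ohio and Washington

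*Combined protocol and SAP*

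**What the plan says.** Section 12.2 opens with "The primary aims are to compare dental care receipt among the five intervention groups, overall and separately for each study site", so the site comparisons belong to the primary aims. It says that the gatekeeper sequence permits a "nominal 0.05 alpha level for each test while maintaining a 0.05 family-wise alpha level for the six tests (three at each study site").

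Section 12.4 describes two gates:

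- **Arm gate.** S vs CSM+DIG is tested first at 0.05. Only if it is significant are S vs CSM and CSM vs CSM+DIG tested, both at 0.05.
- **Site gate.** "We will use a similar approach for testing for each site": each comparison is tested overall, stratified by site, at 0.05, and if significant "we will then test (for the same treatment comparison) the effect within each site (at the 0.05 nominal alpha level").

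The claim then follows: "A 0.05 family-wise error level is attained in this approach assuming that a (true) effect for S vs. CSM+DIG implies" a true effect in at least one of the other two comparisons, and that an overall effect means an effect at one or both sites. No other condition is given. The text does not say whether S vs CSM+DIG must also be significant within a site before that site's other two tests.

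Section 12.4 also plans a site-by-intervention interaction, and "the latter will be tested to formally assess possible intervention effect heterogeneity over sites".

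**The concern.** Taken singly, each gate works. Among three arms, either all three nulls are true or at most one is, so a test of S vs CSM+DIG at 0.05 protects the other two. Within one comparison, a true overall effect leaves at most one null site.

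Crossing the gates breaks this. A real effect at one site can open the overall gates, and the other site's tests then run at 0.05 with several nulls still true. Even with a gate inside each site, each site spends its own 0.05.

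What is at stake is a claim of effect at one site, which is most likely to be made when the sites appear to differ. That is also where the stated error rate fails.

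**Working it through.** **Inputs.** From 12.2: rates 19% (S), 37% (CSM) and 57% (CSM+DIG), 102 caregivers per arm per site, two-sided pooled Z test. From 12.4: every gate and test at 0.05. All other rate patterns below are assumptions, chosen so that both conditions in 12.4 are met.

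**Reproducing the plan's power.** n = [1.96·√(2p̄(1−p̄)) + 0.8416·√(p₁(1−p₁)+p₂(1−p₂))]² / (p₂−p₁)².

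- 19% vs 37%: [1.96·√0.4032 + 0.8416·√0.3870]² / 0.0324 = 96.5, so 97.
- 37% vs 57%: [1.96·√0.4982 + 0.8416·√0.4782]² / 0.04 = 96.6, so 97.

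Allowing 5% transfers, 97/0.95 = 102. At 102, power is 82% for each comparison; at 204 it is 98%, as stated. The sample size is sound. Only the error claim fails to reproduce.

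**Two readings of 12.4.**

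- *Reading 1:* a site test needs the overall S vs CSM+DIG test and the overall test of its own comparison to be significant.
- *Reading 2:* as reading 1, but S vs CSM+DIG must also be significant within that site before its other two tests.

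**Limits from the structure.**

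- Reading 1, one site fully null and all overall gates open: three pairwise tests among three equal arms, each at 0.05. Error = 1 − P(range of three standard normals ≤ 1.96·√2) = 12.2%.
- Reading 2, S = CSM at one site and CSM = CSM+DIG at the other, large effects otherwise: one unprotected true null per site. Error = 1 − 0.95² = 9.75%.

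**Simulation.** 1,000,000 trials per pattern; overall tests stratified by site, pooled Z within site. An error is the rejection of any true site-level null. Rates are S/CSM/CSM+DIG in percent.

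| Site A | Site B | Reading 1 | Reading 2 |
|---|---|---|---|
| 19/37/57 (planned) | 19/19/19 | 8.8% | 4.7% |
| 19/19/57 | 19/19/19 | 10.7% | 6.2% |
| 19/57/57 | 19/19/19 | 11.0% | 6.7% |
| 19/19/57 | 19/57/57 | 9.2% | 9.2% |
| 19/33/47 | 19/19/19 | 7.1% | 3.5% |
| 19/28/38 | 19/19/19 | 5.5% | 2.6% |
| 19/25/30 | 19/19/19 | 3.8% | 2.2% |
| 19/37/57 | 19/19/57 | 2.5% | 2.5% |
| 19/57/57 | 19/57/57 | 3.5% | 3.5% |
| 19/19/19 | 19/19/19 | 3.5% | 3.2% |
| 19/37/57 | 19/37/57 | 0 (no true null) | 0 |

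More extreme assumed rates approach the limits: 5/50/95 with a null site gives 11.9% under reading 1. The three overall tests alone stayed at about 5% or less (at most 5.1%).

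**Unequal sites.** Section 5.3 adds a second recruitment year in Ohio districts only, so the sites may differ in size. For assumed per-arm splits (active/null site) at planned-plus-null, readings 1 / 2 are 10.1% / 4.9% at 138/66, 9.9% / 5.1% at 120/84, 8.1% / 4.0% at 84/120 and 6.6% / 2.8% at 66/138.

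**Siblings.** Section 12.2 says "we expect 10% of caregivers to have multiple (usually two) children"; section 5.3 later uses 30%. A child-level robust score test with 10% or 30% sibling pairs and an assumed within-caregiver correlation of 0.3 or 0.8 gave 8.8–9.3% / 4.7–5.0% for planned-plus-null, 11.0–11.4% / 6.6–6.8% for 19/57/57 plus null, and 8.6–9.2% on both readings for the two opposite patterns.

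**The case against.** The documents give one set of rates and assume them "or 37% versus 57% (as expected for Arm 1 vs Arm 2) for each site". Under those rates no null is true and the error is zero. Exceeding 0.05 needs an exact null at a site together with a strong effect elsewhere; replace the null site by one with small but real differences between all arms and there is nothing to reject falsely. The largest figures come from stark patterns, such as CSM alone doing nothing at one site and everything at the other. Both sites use the same control letter, and the information guide differs only in local resources. Under reading 2 the most natural case, planned effects at one site only, is at or near 0.05. The overall hypothesis in 12.1 is not touched.

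All of that stands as a statement of scope, and it is why this is a correction to make rather than a flaw in the trial. It does not rescue the claim. A family-wise level is a guarantee over every configuration its conditions allow, and every pattern above 0.05 in the table meets both conditions. Under reading 1 the plan's own rates at one site are enough. The plan itself treats heterogeneity between sites as possible.

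**Conclusion.** The 0.05 family-wise level over the six site tests is not guaranteed on either reading of 12.4. At the planned sample size the error is 8.8% (reading 1) or 4.7% (reading 2) with planned effects at one site and none at the other. Over the 14 patterns run with a true site-level null, from which the table is drawn, it is 2.5–11.0% (reading 1) or 2.2–9.2% (reading 2). The excess needs effects that differ between sites. The three overall comparisons keep their error rate.

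The alternative rates, site splits and within-caregiver correlations are assumptions. Covariate adjustment and school-level clustering were not modelled, so the decimals are illustrative. The failure comes from the gate structure, not from the choice of test statistic. This should be fixed, because the site comparisons are a stated primary aim.

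**What to change.** **Main option.** In 12.2 and 12.4, claim 0.05 family-wise error only for the three overall comparisons (S vs CSM+DIG first, then the other two) and delete the claim for the six site tests. Report site contrasts with 95% confidence intervals and nominal p-values beside the planned interaction test. This takes a few sentences and no change in conduct; the site results lose confirmatory status.

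**If confirmatory site claims are kept.** Keep the overall gates at 0.05, test each site at 0.025, and require S vs CSM+DIG to be significant at 0.025 within a site before its other two tests. Within a site, either all three nulls are true and the 0.025 gate must fail first, or at most one is true. Each site is therefore bounded at 0.025, and the six tests at 2 × 0.025 = 0.05 (simulated 1.2–4.5% over the same 14 patterns). State that the three overall tests and the six site tests are two families, each at 0.05; counted as one family of nine, this option reaches up to 6.9%.

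The cost, against reading 1 with planned rates at both sites, is site power of 74% instead of 82% for S vs CSM and 75% instead of 84% for CSM vs CSM+DIG; S vs CSM+DIG stays above 99%. About 118 to 120 per arm per site would restore 80%. The largest losses found were about 21 points (for example S vs CSM, 82% to 61%, with 19/37/37 at both sites).

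A Holm step across sites recovers part of this: if all three tests at one site are rejected at 0.025, the other site may be tested at 0.05. The six-test bound still holds. If both sites have a true null, the first false rejection must occur at 0.025; if only one has, it is bounded at 0.05. At the planned rates, site power is then about 79% for both comparisons.

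Under any option that keeps site testing, 12.4 should say exactly how the two gates combine.
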